12.3 Follow-up of adverse events

All SAEs must be followed up until the outcome of the event is “recovered”, “recovered with sequelae” or “fatal”, and until all queries have been resolved. Cases of chronic conditions, cancer or AEs ongoing at time of death (where death is due to another AE) may be closed with the outcome “recovering” or “not recovered”, when the subject has completed the follow up period.

The follow-up information should only include new (corrections or new or additional) information and should be reported **within 24 hours** of obtaining knowledge of the information. This is also the case for previously non-serious AEs which subsequently become SAEs.

Follow-up information on MESIs (not also fulfilling the SAE criteria) should only include new (corrections or new or additional) information and should be reported **within 14 calendar days** of obtaining knowledge of the information. This is also the case for previously non-serious AEs which subsequently fulfil the MESI criteria.

Non-serious AEs (not also fulfilling the MESI criteria) must be followed until the outcome of the event is “recovering”, “recovered” or “recovered with sequelae” or until the end of the follow-up period stated in the protocol, whichever comes first, and until all queries related to these AEs have been resolved. Cases of chronic conditions or cancer or AEs ongoing at time of death (where death is due to another AE) may be closed with the outcome “recovering” or “not recovered”.

Queries or follow-up requests from Novo Nordisk should be responded to within 14 calendar days.

The investigator must forward follow-up information on SAEs to Novo Nordisk within 24 hours of obtaining the follow-up information by using a new AE form and/or a safety information form marked as follow-up.

The investigator must forward follow-up information on MESIs (not fulfilling the SAE criteria) to Novo Nordisk within 14 calendar days of obtaining the follow-up information by using a new AE form and/or a safety information form and/or MESI form marked as follow-up.

The investigator must forward follow-up information on non-serious AEs (not fulfilling the MESI criteria) as corrections to the original AE form, or by using a new AE form marked as follow-up.

12.4 Technical complaints, and technical complaint samples

12.4.1 Reporting of technical complaints

All technical complaints on the pre-filled pen system (pen and/or needle) of the trial products which occur from the time of first usage of trial supplies until the last usage of trial supplies must be collected and reported to Novo Nordisk.

The investigator must assess whether the technical complaint is related to any AE(s), SAE(s) and/or MESI(s).

Technical complaints must be reported on a separate technical complaint form and must be completed for each trial product listed on the technical complaint form. If the technical complaint involves more than one batch number, a technical complaint form for each batch number must be completed.

The investigator must complete and forward the technical complaint form by fax, e-mail or courier to Novo Nordisk, within the same timelines as for reporting AEs and SAEs as follows:

- Technical complaint assessed as related to an SAE within 24 hours of the trial site obtaining knowledge of the complaint
- All other technical complaints within 5 calendar days

12.4.2 Collection, storage and shipment of technical complaint samples

The investigator must collect the technical complaint sample and notify the monitor within 5 calendar days. The monitor must initiate the shipment to Novo Nordisk and ensure the sample is sent in accordance with local regulations as soon as possible to Novo Nordisk complaint centre. A copy or a print of the technical complaint form should be sent with the sample.

The investigator should ensure that the technical complaint sample contains the batch number and, if available, the DUN.

If the technical complaint sample is unobtainable, the investigator must specify on the technical complaint form why it is unobtainable.

Storage and shipment of the technical complaint sample must be done in accordance with the conditions prescribed for the product (see section 9 and the TMM). The shipment of the technical complaint sample should be done in accordance with the same conditions as for storage.

12.5 Precautions/over-dosage

In the event of over dosage, appropriate supportive treatment should be initiated according to the patient's clinical signs and symptoms.

12.6 Committee related to safety

12.6.1 Novo Nordisk safety committee

Novo Nordisk has constituted an internal safety committee to perform ongoing safety surveillance. The safety committee may recommend unblinding of any data for further analysis, and in this case an independent ad hoc group will be established in order to maintain the blinding of the trial personnel.

13 Case report forms

Paper CRF is used. CRFs will be provided by the sponsor.

Print legibly, using a ballpoint pen. Ensure that all questions are answered, and that no empty data blocks exist. Ensure that no information is recorded outside the data blocks.

If a test/assessment has not been done and will not be available, indicate this by writing “ND” (not done) in the appropriate answer field in the CRF. If the question is irrelevant (e.g., is not applicable) indicate this by writing “NA” (not applicable) in the appropriate answer field. Further guidance can be obtained from the instructions in the CRF.

The investigator must ensure that all information derived from source documentation is consistent with the source information. By signing the affirmation statement, the investigator confirms that the information is complete and correct.

13.1 Correction to CRFs

Corrections to the data in CRFs may only be made by drawing a double straight line through the incorrect data and then writing the correct entry next to the data that were crossed out. Each correction must be initialled (or sealed), dated and explained (if necessary) by the investigator or the investigator’s authorised staff.

If corrections are made by the investigator’s authorised staff after the date of the investigator’s signature on the affirmation statement, the affirmation statement must be signed and dated again by the investigator.

Corrections necessary after the CRFs have been removed from the investigator’s site must be documented on a data clarification form (DCF) or a monitor-initiated discrepancy form (MIDF). If the affirmation statement for the subject has not yet been signed, any corrections must be approved by the investigator or her/his authorised staff. If the affirmation statement for the subject has already been signed, the investigator must approve any correction.

13.2 Case report form flow

The investigator must ensure that data are recorded in the CRF as soon as possible after the visit.

The CRF will consist of two-part NCR (no carbon required) papers. The original is for Novo Nordisk, and the first copy is for the investigator.

The monitor collects the original after the investigator completes the affirmation statement once no further changes are expected.

Protocol
Trial ID: GHLIQUID-4020
UTN: U1111-1131-5892

~~CONFIDENTIAL~~

Date: 21 March 2013
Version: 1.0
Status: Final
Page: 61 of 87

Novo Nordisk

The investigator will receive three copies of each laboratory report except for IGF-I directly from the laboratory in a timely manner. The report of IGF-I will be sent to investigators after the 2nd database lock. The investigators must review the laboratory reports immediately after receipt, and when no further alterations to the contents are expected, date and sign (or put a seal on) on one copy, and retain it at the study site as source data. One copy will be pasted on the appropriate page of the CRFs. The investigator must sign or seal over the joint appropriately.

Data except laboratory data from the original CRF will be entered in the database by the data management unit of the sponsor. All laboratory data will be transferred electronically from the central laboratory to the sponsor. The original kept until a clean database has been obtained and transfer of data has taken place. The original CRF is kept at the sponsor and the first copy is retained at the trial site.

14 Monitoring procedures

During the course of the trial, the monitor will visit the trial site to ensure that the CRFs are completed correctly and the protocol adhered to, to perform source data verification, monitor drug accountability and collect completed CRF pages. Monitoring visit intervals will not exceed 6 weeks until Visit 5 and 18 weeks after Visit 6.

The monitor must be given direct access to source documents (original documents, data and records). Direct access includes permission to examine, analyse, verify and reproduce any record(s) and report(s) that are important to the evaluation of the trial. If the electronic medical record does not have a visible audit trail, the investigator must provide the monitor with signed and dated printouts. In addition the relevant trial site staff should be available for discussions at monitoring visits and between monitoring visits (e.g., by telephone).

The monitor will collect CRF pages and other trial related forms containing data from screening failures.

All data must be verifiable in source documentation other than the CRF, except for the following data that may be recorded directly in the paper CRFs, and will be considered source data:

- Existence of subject (subject identifier, date of birth)
- Confirmation of participation in the trial (subject ID, trial ID, and signed and dated informed consent form(s))
- Diagnosis/indication under investigation
- Visit dates
- Data from:
 - AE form(s)
 - safety information form(s)
 - technical complaints form(s)
- Relevant medical history/concomitant illness
- Reason for exclusion or withdrawal

The daily dosage note data will be included as source data.

If source data are entered in a paper CRF, each data entry or clear series of data entry must be signed and dated separately by the trial staff making the entry.

A detailed diagram and description of the transmission of electronic data should be provided. The source data and their respective capture methods should be clearly defined

There must be a source document agreement at each site.

Monitors must review the medical records and other source data to ensure consistency and/or identify omissions compared to the CRF. If discrepancies are found, the investigator must be questioned about these.

14.1 Medical problem

The investigator should assess whether the medical problem entered into the daily dosage note should be considered an AE. If the medical problem is considered an AE, an AE form must be completed in the CRF, according to section [12.2](#).

15 Data management

Data management is always the responsibility of Novo Nordisk. Data management activities including computer system operations may be delegated under an agreement of transfer of responsibilities to another data management unit within Novo Nordisk.

Laboratory data will be transferred electronically from the central laboratory performing clinical analyses. In the case where laboratory data is transferred via non-secure electronic networks, data will be encrypted during transfer. Details of laboratory data formats and transfer will be specified in a separate written agreement between the laboratories and Novo Nordisk.

The subject and biological material obtained from the subject will be identified by subject ID and trial identification number. Appropriate measures such as encryption or leaving out certain identifiers will be enforced to protect the identity of subjects in all presentations and publications as required by local, regional, and national requirements.

16 Computerised systems

Novo Nordisk will capture and process clinical data using computerised systems which are described in Novo Nordisk standard operating procedures (SOPs) and IT architecture documentation. The use and control of these systems are documented.

The investigators working on the trial may use their own electronic systems to capture source data. Novo Nordisk will collect information on the practical use of these systems within the conduct of this clinical trial.

17 Statistical considerations

If necessary, a statistical analysis plan (SAP) may be written in addition to the protocol, including a more technical and detailed elaboration of the statistical analyses. The SAP will in that case be finalised before database lock.

Analyses of all efficacy endpoints will be performed based on the full analysis set (FAS). The primary analysis of the primary endpoint will be repeated on the per protocol (PP) analysis set.

Safety endpoints will be summarised using the safety analysis set (SAS).

The impact of protocol deviations and outliers may be investigated further in sensitivity analyses if deemed relevant.

Missing values for endpoints other than OGTT, HbA_{1c} and bone age will be imputed using the last observation carried forward (LOCF) method.

All endpoints will be summarised descriptively at each visit by treatment using observed data. After 104 weeks of treatment, descriptive statistics will be presented based on both observed and LOCF imputed data. Endpoints that are analysed untransformed and endpoints that are not formally analysed are summarised by the arithmetic mean, standard deviation (SD), median, and minimum and maximum value. Endpoints that are analysed log-transformed are summarised by the geometric mean, coefficient of variation (CV), median, minimum and maximum value.

LOCF imputed data will be used as the basis for plotting data.

A formal statistical test will only be performed at 104 weeks. Presentation of results from a statistical analysis will include the estimated mean treatment effects (LSMeans). Estimated mean treatment differences (or ratios) will be presented together with two-sided 95% confidence intervals and p values for all endpoints analysed statistically.

For endpoints measured over time mean values will be plotted to explore the trajectory over time. Data collected before randomisation will only be summarised descriptively.

Statistical analysis will be performed twice, at 104 weeks and at the end of trial including extension phase.

17.1 Sample size calculation

The primary endpoint is change in height SDS from baseline to 104 weeks of treatment¹⁷. Since the primary objective of this trial is to evaluate the growth promoting effect of NN-220, the following hypothesis will be statistically tested; $H_0: \mu_1 = \mu_2$ vs. $H_1: \mu_1 \neq \mu_2$, where μ_i is the population mean, i

=1, 2 represents the 0.033 mg/kg/day and 0.066 mg/kg/day, respectively. Primary analysis for primary endpoint will be performed based on the analysis of covariance (ANCOVA) model with treatment as a fixed effect and baseline height SDS as a covariate.

The sample size is calculated using two sided two sample t-test for $\mu_1 = \mu_2$ with a 5% significance level.

According to Osio D., et al. (2005)⁷, the mean (SD) of change in height SDS of treatment with 0.033 mg/kg/day and 0.066 mg/kg/day from baseline was 0.8 (0.4) after 1 year and a further mean gain of 0.4 (0.7) was observed after 2 years (mean and SD for each treatment are not presented in the article). In the GHLiquid-1516 trial (Japanese subjects with short stature born small for gestational age), mean difference of height SDS between 0.033 mg/kg/day and 0.067 mg/kg/day was 0.6 at 104 weeks. The results of the sample size calculations with power 80% can be seen in [Table 17-1](#) for different SDs and mean treatment differences that can be detected.

Table 17-1 Sample size per treatment group with power 80%

		Mean difference of 0.033 mg/kg/day and 0.066 mg/kg/day					
SD	0.35	0.40	0.45	0.50	0.55	0.60	
0.40	22	17	14	12	10	9	
0.45	27	21	17	14	12	10	
0.50	34	26	21	17	15	12	
0.55	40	31	25	21	17	15	
0.60	48	37	29	24	20	17	

With mean difference $\mu_2 - \mu_1 = 0.45$ and $SD = 0.5$, 21 subjects per treatment group give power 80%. In the GHLiquid-1516 trial, withdrawal rates were 6.1% and 5.9% for 0.033 mg/kg/day and 0.067 mg/kg/day, respectively. Assuming 10% of withdrawal rate from this result, sample size was determined as 24 per treatment group in order to ensure the power on PP analysis set. Thus, the sample size of 48 subjects in total is set, assuming exclusion of 6 subjects from PP analysis set.

17.2 Definition of analysis sets

The following analysis sets are defined in accordance with the ICH-E9 guidance²⁶:

- Full analysis set (FAS): includes all randomised subjects. In exceptional cases subjects from the FAS may be eliminated. In such cases the elimination will be justified and documented. The statistical evaluation of the FAS will follow the intention-to-treat (ITT) principle and subjects will contribute to the evaluation “as randomised”.

- The PP analysis set will consist of all subjects in the full analysis set who fulfils the following criteria:
 - Have not violated any inclusion criteria
 - Have not fulfilled any exclusion criteria
 - Have a non-missing height at baseline
 - Have at least 52 weeks of treatment
 - Have at least one non-missing height after 52 weeks of treatment

Subjects in the PP set will contribute to the evaluation “as treated”.

- Safety analysis set: includes all subjects receiving at least one dose of investigational medicinal product (0.033 mg/kg/day and 0.066 mg/kg/day of NN-220). Subjects in the safety analysis set will contribute to the evaluation “as treated”.

Randomised subjects who are lost to follow up and where no information on exposure is available after randomisation will be handled as unexposed.

The decision to exclude any subject or observation from the statistical analysis is the joint responsibility of the study group members. The subjects or observations to be excluded and the reason for their exclusion will be documented and signed by all parties, prior to the database lock. The subjects and observations excluded from analysis sets, and the reason for this, will be described in the clinical trial report.

17.3 Primary endpoint

The primary endpoint is change in height SDS from baseline to 104 weeks of treatment¹⁷.

Statistical analysis

Since the primary objective of this trial is to evaluate the growth promoting effect of NN-220, the following hypothesis will be statistically tested; $H_0: \mu_1 = \mu_2$ vs. $H_1: \mu_1 \neq \mu_2$, where μ_i is the population mean, $i = 1, 2$ represents 0.033 mg/kg/day and 0.066 mg/kg/day, respectively. Primary analysis for the primary endpoint will be performed based on the ANCOVA model with treatment as a fixed effect and baseline height SDS as a covariate.

Sensitivity analysis

The same analysis as for the primary endpoint will be repeated on the PP analysis set.

All height SDS measurements at scheduled time points after randomisation will be analysed in a linear mixed model with treatment, time and interaction between treatment and time as fixed effects, baseline height SDS and interaction between baseline and time as a covariate and subject as a

random effect. This approach assumes that data are missing at random according to the taxonomy defined by Rubin (1976)²⁷. Treatment differences at 104 weeks will be estimated using this model.

Any marked difference concerning treatment differences between the sensitivity results and the result from the primary endpoint will be commented upon in the CTR.

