- Criterion 4; Children beyond infancy and 3 years age or older are eligible as subjects. Therefore, the minimum age was set at 3 years old. In addition, it is difficult to judge the efficacy of NN-220 administration in children who have developed secondary sexual characteristics. Puberty is typically delayed for both boys and girls with Noonan syndrome. The mean age of puberty onset is 13.5 to 14.5 years in boys and 13 to 14 years in girls¹³. The upper limit of the subjects is set less than 11 years for boys and less than 10 years for girls taking the treatment period into consideration.
- Criterion 5 is applied because this data is essential to compare the growth promoting effect of NN-220 after administration with that of pre-treatment.
- Criterion 6 is set because it is difficult to evaluate the efficacy of NN-220 in children who have developed secondary sexual characteristics.

Table 6-1 Diagnostic criteria for Noonan syndrome* (van der Burgt score list)

Feature	A = major	B = minor
1 Facial	• Typical face ¹⁾	• Suggestive face
2 Cardiac	• Pulmonary valve stenosis and / or typical ECG ²⁾	• Other defect
3 Height	• < 3rd centile (-1.88 SDS)	• < 10th centile (-1.28 SDS)
4 Chest wall	• Pectus carinatus / excavatum	• Broad thorax
5 Family history	• First degree relative definite Noonan syndrome	• First degree relative suggests Noonan syndrome
6 Other	• All 3 (males): mental retardation, cryptorchidism, lymphatic dysplasia	• One of mental retardation, cryptorchidism, lymphatic dysplasia

* Definite Noonan syndrome: 1A plus one of 2A-6A or two of 2B-6B; 1B plus two of 2A-6A or three of 2B-6B.

¹⁾ The typical facial anomalies consist of a broad forehead, hypertelorism, ptosis, down-slanting palpebral fissures, micrognathia, apparently lowset, posteriorly angulated ears with a thick helix and a broad short neck.

²⁾ The typical ECG is characterized by an abnormal R/S ratio over the left precordial leads, wide QRS complexes, left-axis deviation and a giant Q wave.

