8.1.3 Visit 1 (screening visit)

It will be confirmed that the subjects must attend Visit 1 fasting, having consumed only water from 9 pm in the previous evening for the OGTT.

At screening, the subjects will be assigned a unique subject identification (ID) which will remain the same throughout the trial. The subject ID will consist of 4 digits (the first 2 digits indicating the site number and the last 2 digits indicating the subject number).

A screening session should be performed in the IV/WRS in order to register the subject in the system.

The following will be performed and/or recorded in the case report form (CRF) in addition to what is described in the flowchart and in the assessment sections (sections [8.2](#), [8.3](#), [8.4](#), [8.5](#) and [8.6](#)).

- Signed informed consent(s)
 - Date
 - Time (if consent and trial procedures occur on the same day the clock time must be recorded)
- Inclusion and exclusion criteria (sections [6.2](#) and [6.3](#))
- Demography:
 - Date of birth
 - Sex
- Diagnosis of Noonan syndrome according to van der Burgt score list ([Table 6-1](#)), the date of diagnosis and the name of investigators who made diagnosis

- Genotype of Noonan syndrome (In case genetic testing for Noonan syndrome had been performed at the time of diagnosis before Visit 1 and genotype of Noonan syndrome is revealed.)
 - PTPN11
 - KRAS
 - SOS1
 - RAF1
 - BRAF
 - SHOC2
 - NRAS
- Height data within the period between 40 to 64 weeks prior to Visit 1 and the date of measurement
- Medical history of other diseases related to the trial as judged by the investigator

Screening failures

If the subject is ineligible to participate in the trial the subject will be considered a screening failure. Consequently, a screening failure session must be performed using the IV/WRS, a screening failure form must be completed with the reason for not continuing in the trial.

Adverse events from screening failures must be transcribed by the investigator into the case report form (CRF). Follow-up of adverse events should be carried out according to section [12](#).

When trial-related procedures have been finalised for screening failures, no more AEs should be recorded in the CRF.

8.1.4 Visit 2 to the visit before Visit 20

Randomisation should be performed after subject eligibility is confirmed and before procedures at Visit 2.

Visit 2 will take place within 4 weeks after Visit 1.

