8.4 Assessments for efficacy

8.4.1 Height

Height must be measured three times (without shoes and socks) in total at all visits. Subjects should step away from the height measurer between each measurement. Each measurement will be recorded in centimetre in the CRF and recorded to one decimal place.

A height data within the period between 40 and 64 weeks prior to Visit 1 (screening) is used for assessment for efficacy as a control data. The height had been measured during normal management of subjects.

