17.4 Secondary endpoints

17.4.1 Efficacy parameters

Efficacy parameters are as follows.

- Height velocity SDS from baseline to 52 weeks of treatment²⁸
- Height velocity SDS from 52 weeks to 104 weeks of treatment²⁸
- Height velocity from baseline to 52 weeks of treatment
- Height velocity from 52 weeks to 104 weeks of treatment

Statistical analysis

Efficacy parameters will be summarised and graphically presented.

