1.2 Scope of the statistical analysis plan

This Statistical Analysis Plan (SAP) is based on the statistical analyses of GHLIQUID-4020 as planned in the trial protocol.

Changes to the statistical methods proposed in this SAP and the reason for the change must be reported in the clinical trial report (CTR).

This SAP is based on the protocol version 2.0 (Dated 03 March 2016).

2 Statistical considerations

Analyses of all efficacy endpoints will be performed based on the full analysis set (FAS). The primary analysis of the primary endpoint will be repeated on the per protocol (PP) analysis set.

Safety endpoints will be summarised using the safety analysis set (SAS).

The impact of protocol deviations and outliers may be investigated further in sensitivity analyses if deemed relevant.

Missing values for endpoints other than OGTT, HbA_{1c} and bone age will be imputed using the last observation carried forward (LOCF) method.

All endpoints will be summarised descriptively at each visit by treatment using observed data. After 104 weeks of treatment, descriptive statistics will be presented based on both observed and LOCF imputed data. Endpoints that are analysed untransformed and endpoints that are not formally analysed are summarised by the arithmetic mean, standard deviation (SD), median, and minimum and maximum value. Endpoints that are analysed log-transformed are summarised by the geometric mean, coefficient of variation (CV), median, minimum and maximum value.

LOCF imputed data will be used as the basis for plotting data.

A formal statistical test will only be performed at 104 weeks. Presentation of results from a statistical analysis will include the estimated mean treatment effects (LSMeans). Estimated mean

treatment differences (or ratios) will be presented together with two-sided 95% confidence intervals and p values for all endpoints analysed statistically.

For endpoints measured over time mean values will be plotted to explore the trajectory over time. Data collected before randomisation will only be summarised descriptively.

Statistical analysis will be performed twice, at 104 weeks and at the end of trial including extension phase.

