2.4 Secondary endpoints

2.4.1 Efficacy endpoints

Secondary efficacy endpoints are as follows.

- Height velocity SDS from baseline to 52 weeks of treatment^v
- Height velocity SDS from 52 weeks to 104 weeks of treatment
- Height velocity from baseline to 52 weeks of treatment
- Height velocity from 52 weeks to 104 weeks of treatment

Statistical analysis

Secondary efficacy endpoints will be summarised and graphically presented.

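### The stated objective is growth promotion by NN-220, but every treatment-effect test on height SDS compares the two doses, and the pre-treatment height collected as control data enters no specified comparison

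*Protocol*

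**What the plan says.** The primary objective (Protocol 4.1.1, SAP 1.1) is to evaluate how far NN-220 promotes growth over 104 weeks. It is not worded as a dose comparison. Protocol 17.3 turns it into a test as follows: "Since the primary objective of this trial is to evaluate the growth promoting effect of NN-220, the following hypothesis will be statistically tested", namely equality of the two dose-group means. Protocol 17.1 and SAP 2.3 say the same. The per-protocol repeat, the mixed model and the SAP's added analysis on the Noonan reference also estimate the difference between doses.

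On reporting, the opening text of Protocol section 17 says "Estimated mean treatment differences (or ratios) will be presented together with two-sided 95% confidence intervals and p values for all endpoints analysed statistically". LSMeans and by-arm descriptive statistics are planned, with no interval attached. The exploratory ANCOVA in SAP 2.3 adds intervals for sex, age and baseline height SDS only.

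The pre-treatment height is treated quite differently in the clinical sections:

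- Rationale for the inclusion criteria (Protocol 6.2): "Criterion 5 is applied because this data is essential to compare the growth promoting effect of NN-220 after administration with that of pre-treatment".
- Protocol 8.4.1: this height "is used for assessment for efficacy as a control data".
- Protocol 8.1.3 collects "Height data within the period between 40 to 64 weeks prior to Visit 1 and the date of measurement".

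The analysis text in SAP section 2 (and Protocol section 17) says "Data collected before randomisation will only be summarised descriptively". Height velocity is defined for two periods only, "Height velocity from baseline to 52 weeks of treatment" and the following 52 weeks, and SAP 2.4.1 says "Secondary efficacy endpoints will be summarised and graphically presented".

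**The concern.** The step from objective to hypothesis does not follow. With no placebo or untreated arm (Protocol 5.2), equality of two active doses says nothing about whether either promotes growth. The protocol's substitute for a control is the child's own earlier growth. It makes the earlier height an eligibility requirement for that reason and then leaves it out of the analysis plan.

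The dose rationale in Protocol 5.4 rests on change in height velocity: 2.2 cm/year in the Japanese phase 2 trial, and 3.5 and 5.4 cm/year at the two doses in Sweden. The plan never defines that quantity for this trial.

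If the dose difference is not significant, the report would have no pre-specified inference on the objective, even if both arms gained more than 1 SDS. A comparison with pre-treatment growth would then have to be designed after the codes are opened to the sponsor, which Protocol 11.2 places after the first database lock.

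**Working it through.** **Inputs.** From Protocol 17.1: two-sided two-sample t-test at 5%, difference 0.45, SD 0.5, 21 per group for 80% power, 24 per group after allowing for withdrawal. From the published Swedish data cited there, doses pooled: mean gain 0.8 (SD 0.4) in year 1 and a further 0.4 (SD 0.7) after year 2. From the SGA trial cited there: a dose difference of 0.6.

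**1. The plan's own figure.** Power comes from the noncentral t with 2n − 2 df and noncentrality δ / (σ√(2/n)). At n = 21 this is 0.45 / (0.5 × √(2/21)) = 2.92, giving power 81.2%. All 30 cells of Table 17-1 reproduce, and 21 / 0.9 = 23.3 rounds up to 24. The sample size for the dose comparison is correct.

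**2. How often the planned test is non-significant.**

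| Dose difference | SD | Power, n = 21 / 24 per arm | Chance of non-significance |
|---|---|---|---|
| 0.45 (planning value) | 0.5 | 81% / 86% | 14–19% |
| 0.6 (SGA trial) | 0.5 | 97% / 98% | 2–3% |
| 0.45 | 0.6 | 66% / 72% | 28–34% |
| 0.45 | 0.8 | 43% / 48% | 52–57% |
| 0.2 (illustrative, not in the documents) | 0.5 | 24% / 27% | 73–76% |
| 0 (equal effect) | any | 5% / 5% | 95% |

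The SDs of 0.6 and 0.8 reflect the cited components. SD of the two-year change = √(0.4² + 0.7² + 2r × 0.4 × 0.7), which is 0.61, 0.81 and 0.96 at r = −0.5, 0 and 0.5. The correlation r is an assumption. The component SDs are pooled over doses, so the SD within a dose would be slightly lower.

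**3. Precision of a within-dose interval.** The half-width is t(0.975, n − 1) × SD / √n. At n = 21: 2.086 × 0.5 / √21 = 0.23 SDS, and 0.36 at SD 0.8. At the largest SD that the components allow (r = 1, SD 1.1) it is 0.50. The cited two-year gain is 0.8 + 0.4 = 1.2 SDS.

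**4. Precision of the comparison with pre-treatment growth.** The documents give no SD for the paired change in height velocity. Assuming 1.5 to 3 cm/year, the half-width at n = 21 is 2.086 × 1.5 / √21 = 0.68 up to 2.086 × 3 / √21 = 1.37 cm/year. The Swedish changes cited in Protocol 5.4 are 3.5 and 5.4 cm/year.

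**5. Is the pre-treatment comparison computable?** Yes. The earlier height is recorded with its date, and height is measured again at Visit 1. Actual dates allow annualisation despite the 40-to-64-week window.

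**The case against.** The strongest reply is that the trial is a dose comparison by design. Protocol 5.2 gives that as the purpose of the parallel groups, the doses were chosen for different expected efficacy, and the protocol regards the growth effect as already shown in Sweden. An objective to evaluate an effect can be met by estimation, and a significant dose difference would itself indicate that at least one dose works. This justifies keeping the dose test primary. It does not provide inference on the objective if the doses are similar, and it does not explain why the control height is unused.

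A second reply is that a within-dose interval for height SDS involves little post hoc discretion, because endpoint, time point, analysis set, LOCF, mean, SD and LSMeans are already fixed. With an expected gain near 1.2 SDS, that interval would very probably exclude zero, and it is uncontrolled. This largely stands, so the weight of the point rests on the missing comparison with pre-treatment growth, where neither the measure nor the interval is defined.

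Third, the descriptive-only rule could be read as settling how the earlier height is treated, and descriptive velocities might satisfy the stated purpose. But no summary of pre-treatment growth is listed either.

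Finally, the power figures at SD 0.6 and 0.8 partly concern the sample-size assumption. That is fair. On the planning SD the non-significance risk at 0.45 is 14 to 19%.

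**Conclusion.** The concern holds and should be fixed. The primary test is valid for comparing doses and its sizing is correct, but the objective as worded has no pre-specified inference of its own. Followed as written, the plan also leaves unused the comparison for which the earlier height is required.

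The gap matters when the dose difference is not significant. That has a 14 to 19% chance at the planning values and 2 to 3% at a difference of 0.6. It exceeds one half if the two-year SD is about 0.8, which depends on the assumed correlation between yearly gains. If both doses work equally well, it is 95%.

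By-arm means, LSMeans and the Noonan-reference SDS will still describe growth in each arm. What is missing is stated precision within a dose and a defined comparison with growth before treatment.

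**What to change.** Keep the dose comparison as the primary test. In SAP 2.3 and 2.4.1, before the first database lock, pre-specify for each dose:

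1. The mean change in height SDS at 104 weeks with a 95% confidence interval.
2. The paired difference between growth over weeks 0 to 52 and annualised growth from the earlier height to Visit 1, using actual measurement dates, with a 95% confidence interval. Report it as height velocity and as an age-standardised measure (height velocity SDS or change in height SDS), since velocity changes with age.

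Exempt item 2 from the descriptive-only rule for pre-randomisation data. Label it as non-randomised and as resting on a routine-care height.

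The cost is SAP wording and two tables. No new data, extra subjects or change to the primary analysis are needed. The drawback is an uncontrolled contrast that sets a height from normal management against triplicate trial measurements, so it can support the dose comparison but not replace it.
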